10.6.4 Exploratory Patient Reported Outcomes objectives

The exploratory patient reported outcomes objectives are:

- To compare the impact of treatment on health care resource utilization between treatment arms in all patients
- To compare the impact of treatment on patient reported outcomes (PRO) including CML-specific symptoms, patient quality of life, and impact on work productivity and activity impairment from baseline through end of treatment between treatment arms in all patients

10.6.4.1 Resource Utilization

Data relating to Resource Utilization from the FAS will be used for the purpose of economic evaluation. Descriptive statistics of the levels of resource utilization over time will be done for each treatment arm. The measures of healthcare Resource Utilization (RU) include: hospitalization (H), Emergency Room (ER) visit, general practitioner (GP) visits, specialist (Sp) visit and urgent care (UC) visit. Medical resource utilization (MRU) will be assessed as follows: frequency and duration of hospitalization from Baseline up to End of Study; frequency of emergency room visits from Baseline up to End of Study; frequency of

[REDACTED]

additional outpatient office visits general practitioner, specialist, and urgent care visits from Baseline up to End of Study. Hospitalization visits will also record the number of days on ward and the type of ward (hospital unit) and the discharge status. At each RU collected, the reason for the visit, i.e. related to CML, AE or other reason, will be collected, in order to quantify the impact of treatment on healthcare resources.

10.6.4.2 Patient Reported Outcomes

The MDASI CML, PGIC along with EQ-5D-5L will be used to compare data on the patient's disease-related symptoms and health-related quality of life from baseline to EOT between the treatment arms. The WPAI will be used to assess work productivity and activity impairment related to the patient's CML. All measures will assess differences between the treatment arms.

Patients with an evaluable baseline score and at least one evaluable post baseline score during the treatment period will be included in the change from baseline analyses. Missing data items in a scale will be handled according to the manual for each instrument. No imputation will be applied if the total or subscale scores are missing at a visit.

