The M.D. Anderson Symptom Inventory – Chronic Myeloid Leukemia (MDASI-CML) is a 26 item self-administered questionnaire for adult CML patients. Twenty of the items measure the severity of disease-related symptoms and are scored from 0 (Not present) to 10 (As Bad as you can imagine) and 6 items that measure symptom interference with daily life scored from 0 (Did not interfere) to 10 (Interfered completely). Descriptive statistics will be provided for the MDASI-CML symptom score and interference score, and the change in the MDASI-CML symptom score and interference score from baseline to all available time points to the end of study. Additional analysis may be performed and details will be described in the analysis plan.

EQ-5D-5L

EQ-5D-5L is a two-part standardized instrument for measuring health outcomes in a wide range of health conditions and treatments. It consists of a descriptive system and a visual analogue scale (EQ VAS). The descriptive system comprises the following 5 dimensions: mobility, self-care, usual activities, pain/discomfort and anxiety/depression. Each dimension has 5 levels: no problems, slight problems, moderate problems, severe problems and extreme problems (or unable to perform the activity). The EQ VAS records the respondent’s self-rated health on a vertical, visual analogue scale where the endpoints are labeled ‘Best imaginable health state’ and ‘worst imaginable health state’. The health states derived from the descriptive system can be summarized into a single index score that provides a simple measure of health for clinical and economic appraisal. Descriptive statistics will be provided for EQ-5D-5L health index score and for the EQ VAS, at each scheduled assessment time point. There should be only ONE response for each dimension. Missing values can be coded as ‘9’. Ambiguous values (e.g. 2 boxes are ticked for a single dimension) should be treated as missing values. Additional analysis may be performed and details will be described in a separate analysis plan.

WPAI

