The Work Productivity and Activity Impairment Questionnaire (WPAI) is a four-item questionnaire which is intended to measure work and activity impairment associated with CML for those who self-identify as currently employed for pay. This questionnaire measures self-reported productivity loss associated with CML during the past seven days. It consists of questions about absence from work due to CML, hours spent at work, the reduction in productivity at work attributed to CML, and the reduction in productivity while performing regular activities. WPAI outcomes are expressed as impairment percentages, with higher numbers indicating greater impairment and less productivity, i.e., worse outcomes. Scoring will be done according to WPAI instrument guidance resulting in four scores including: Percent work time missed due to problem; percent impairment while working due to problem; Percent overall work impairment due to problem; and, percent activity impairment due to problem. Change from baseline in WPAI at each visit, where measured, will be done for each of the four derived scores.

PGIC

The Patient Global Impression of Change is comprised of a single question intended to measure a patient's perspective of improvement or deterioration over time relative to treatment. The PGIC uses a seven-point scale where one (1) equals very much improved and seven (7) equals very much worse. A summary of Patient Global Impression of Change (PGIC) at each visit, where measured will be provided.

8 Safety monitoring and reporting

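### The available protocol text compares patient-reported outcomes between arms by descriptive, on-treatment, observed-case change scores; a baseline-adjusted repeated-measures model at visits already scheduled would be more precise at almost no cost

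*Combined protocol and SAP*

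**What the plan says.** The full text available is protocol Amendment 1. Section 10.6.4 gives the exploratory objective as a comparison of treatment impact on PROs between the arms in all patients. Section 10.6.4.2, like 7.2.6, sets the frame as symptoms and "health-related quality of life from baseline to EOT between the treatment arms". The inclusion rule is that those who have "an evaluable baseline score and at least one evaluable post baseline score during the treatment period will be included in the change from baseline analyses", and "No imputation will be applied if the total or subscale scores are missing at a visit".

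Section 7.2.6 then goes instrument by instrument:

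- **MDASI-CML:** "Descriptive statistics will be provided for the MDASI-CML symptom score and interference score", and for the change in "symptom score and interference score from baseline to all available time points to the end of study".
- **EQ-5D-5L:** descriptive statistics for the "health index score and for the EQ VAS, at each scheduled assessment time point".
- **WPAI:** "Change from baseline in WPAI at each visit, where measured, will be done for each of the four derived scores".
- **PGIC:** a summary by visit. Amendment 2 removed its screening administration, so it has no baseline.

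Further MDASI-CML and EQ-5D-5L analyses are deferred to an analysis plan.

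**The concern.** The text promises a comparison between arms but describes only summaries. It names no model, covariate, reference visit or missing-data assumption. Two separate weaknesses follow.

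- **EOT is not a common time point.** Sections 6.1.5 and 7.1.4 fix no treatment duration per patient, and section 7.1.6 makes discontinuation mandatory on treatment failure. Amendment 3 adds a switch route for bosutinib failures only, and its switch-phase schedule (Table 7-2) shows no PRO rows. An EOT contrast can therefore set early scores in one arm against late scores in the other.
- **By-visit means drop those who have stopped.** If the arms lose patients at different rates, and leavers differ from stayers, the arms are compared on differently selected groups.

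Unequal loss is plausible. Section 2.2 cites diarrhea in 78.5% and vomiting in 37.1% on bosutinib, and section 10.8 designs for MMR rates of 15% and 35%. No discontinuation rate by arm is given.

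At stake is how far an exploratory PRO comparison can be read as applying to all randomised patients, and how precise it is.

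**Working it through.** **1. The plan's own figure.** No PRO sample size, SD, correlation or power is stated. The only design figure that bears on this is section 10.8: 148 + 74 = 222, for 15% against 35%, two-sided 5%, 90% power, 2:1. With pooled variance and no continuity correction, the pooled rate is (0.15 + 2 × 0.35)/3 = 0.2833, and

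n(bosutinib) = [1.960 × √(1.5 × 0.2833 × 0.7167) + 1.282 × √(0.15 × 0.85 + 0.35 × 0.65/2)]² / 0.20² = 73.2, rounded up to 74; total 3 × 74 = 222.

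The figure reproduces. It contains no allowance for dropout.

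**2. Precision.** For common SD σ and baseline correlation r, a change score has variance 2σ²(1 − r) and a baseline-adjusted score has σ²(1 − r²). The ratio is (1 + r)/2. The detectable difference at 80% power is (1.960 + 0.842) × √(1/74 + 1/148) = 0.399, times the square root of 2(1 − r) or of 1 − r². The correlations are assumed, and all 222 patients are taken as evaluable.

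| r | Variance ratio | Detectable, change score (SD) | Detectable, adjusted (SD) |
|---|---|---|---|
| 0.4 | 0.70 | 0.437 | 0.366 |
| 0.5 | 0.75 | 0.399 | 0.345 |
| 0.6 | 0.80 | 0.357 | 0.319 |
| 0.7 | 0.85 | 0.309 | 0.285 |

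**3. By-visit means.** If a fraction d of an arm has left, and leavers would have been g points worse than stayers, the stayers' mean looks better than the whole arm by d × g. The arm difference shifts by (d_B − d_A) × g. Assume 25% of asciminib and 50% of bosutinib patients off treatment by Week 48, and g of 0.5 to 1.5 points on the 0–10 MDASI-CML scale. The shift is 0.25 × 0.5 = 0.13 to 0.25 × 1.5 = 0.38 points in favour of bosutinib. With equal rates, or g = 0, it is zero.

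**4. EOT against a fixed visit.** A large-sample simulation with no true arm effect assumed r = 0.6 between all pairs of visits and the same 0.5 SD improvement in both arms by Week 48. Arm A has fewer leavers. Entries are A minus B in SD on a scale where lower is better, so a negative value flatters A. Simulation error is about 0.005 to 0.01.

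| Nominal % off treatment, A / B | Leaving depends on | Last on-treatment score | Observed-case change, Week 48 | Likelihood-type estimate, Week 48 |
|---|---|---|---|---|
| 20 / 20 | any of the below | within 0.01 | within 0.01 | within 0.01 |
| 20 / 40 | nothing | −0.02 | 0.01 | 0.01 |
| 20 / 40 | last observed score | −0.07 to −0.09 | about 0 | −0.01 to 0 |
| 20 / 40 | unobserved next score | −0.03 to −0.01 | 0.01 to 0.02 | 0.02 to 0.04 |
| 20 / 60 | nothing | −0.08 | about 0 | about 0 |
| 20 / 60 | last observed score | −0.14 to −0.16 | −0.01 to 0.02 | 0 to 0.01 |
| 20 / 60 | unobserved next score | −0.05 to −0.03 | 0.04 | 0.07 to 0.09 |

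Three readings follow.

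- The EOT contrast is biased by timing alone when rates differ (−0.08 SD at 20/60). It is worse when leaving follows the last observed score.
- The fixed-visit likelihood estimate is close to zero when leaving depends only on observed scores. It is not better than the alternatives when leaving depends on an unseen score.
- Observed-case change at Week 48 was nearly unbiased when leaving followed observed scores. The assumed equal correlation between all visits explains this: baseline and Week 48 relate equally to the score that drives leaving. This removes any claim from these runs that a model beats by-visit change on bias.

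**The case against.** The strongest reply is that fixed visits are already planned. MDASI-CML, EQ-5D-5L, WPAI and PGIC all have by-visit summaries, Table 3-1 words the MDASI-CML and EQ-5D-5L endpoints as change over time, and section 10.6.4 can be read as describing a period rather than one contrast at EOT. A reader might infer that the arms are compared only by raw change to EOT. The documents do not support that, and nowhere prescribe pooling early and late exit scores.

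A reader might also infer that only patients still on treatment are analysed. The rule requires a baseline and "at least one evaluable post baseline score during the treatment period will be included in the change from baseline analyses". A patient who leaves after one such score is included, and disappears only from later visit means.

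Further points stand. Many mandatory exits in section 7.1.6 rest on BCR-ABL ratio, cytogenetics or mutations, so leavers need not be the more symptomatic patients. Under randomisation, baseline adjustment mainly buys precision. The objective is exploratory and carries no alpha. The available Amendment 3 text ends within section 7.1.2, and the deferred analysis plan was not available. The Amendment 2 and 3 change lists mention no change to section 10.6.4.2, but a model specified elsewhere cannot be excluded.

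What survives is that the available text names no baseline-adjusted or longitudinal model, although every measure is meant to assess differences between arms.

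**Conclusion.** The point holds as a low-severity improvement to the analysis. The dependable benefit is a variance 15% to 30% below that of change scores, for an assumed baseline correlation of 0.7 down to 0.4, with the same patients and visits.

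It is tempting to add that the model is also less biased. The documents give no discontinuation rates by arm and no PRO variance or correlation, and that claim fails when leaving depends on unobserved scores. The 0.13 to 0.38 point shift and the simulated biases are illustrations under assumed rates. They even point in opposite directions: in these runs an EOT contrast favoured the arm with fewer leavers, while loss of worse-off patients from by-visit means favours the arm with more. No net direction for this trial can be asserted. The primary endpoint, alpha and N = 222 are unaffected.

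**What to change.** State in the SAP, unless its current version already does so:

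- **Model.** For MDASI-CML, EQ-5D-5L and WPAI, a repeated-measures model on scheduled post-baseline scores to Week 48 with arm by visit, baseline by visit and the randomisation stratum (major cytogenetic response or not). Read the arm difference at Weeks 24 and 48. Those two visits are a proposal and should be fixed before data are seen.
- **Scope.** Fit the WPAI work items in employed patients only and label them as such. Leave PGIC out of the model, since it has no baseline.
- **EOT scores.** Descriptive only, shown with time on treatment.
- **Completion.** Tabulate by arm and visit, separating missed questionnaires from stopped treatment.
- **Sensitivity.** Apply a stated range of worse scores after stopping, by arm, and report where the conclusion changes. This probes informative dropout but does not remove it. Collecting PROs after discontinuation would do more, but it is not free and is not proposed here.

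The cost is SAP wording and modest programming, with no new patients, visits or data.

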10.7 Interim analysis

No formal interim analysis is planned for this trial. As described in [Section 10](#), three formal analyses are planned: the primary at week 24, another at the 96-week end of study treatment and a PFS/OS update at year 5.

[figure not shown]
- 24-week primary analysis: Formal testing of the primary endpoint with full alpha will be performed. Analyses of other efficacy endpoints at and by 24 weeks will also be performed.
- 96-week end of study treatment analysis: Formal statistical testing of the key secondary endpoint will be performed with $\alpha = 0.05$ (two-sided) only if the primary endpoint is significant. Analyses of other efficacy endpoints (including MMR rate at 48 weeks) will also be performed.
- 5-year PFS/OS update analysis: PFS and OS

In addition DMC safety analyses will be conducted as described in [Section 8.6](#).

10.8 Sample size calculation

To test the null hypothesis that the response rate is equal in the two groups, based on two-sided 5% level of significance and with 90% power, 222 patients will be needed in total (i.e. 148 patients in the ABL001 arm and 74 patients in the bosutinib arm based on 2:1 randomization allocation). This assumes that ABL001 leads to a 20% improvement in the MMR rate at 24 weeks over bosutinib from 15% to 35% which corresponds to an odds ratio of 3.05.

The assumed bosutinib MMR rate of 15% at 24 weeks is based on previous trials evaluating bosutinib therapy ([Khoury 2012](#), [Gambacorti-Passerini 2014](#), [García-Gutiérrez 2015](#)).

10.9 Power for analysis of key secondary variables

If the primary analysis of MMR rate at 24 weeks is statistically significant, then the key secondary endpoint MMR rate at 96 weeks will be tested, with the overall alpha controlled at the 5% two-sided level. The testing will use a gatekeeping strategy. Full details of the testing strategy are provided in [Section 10.5.1](#).

[Table 10-2](#) below summarizes the treatment effects of the key secondary endpoint which can be detected with 80% and 90% power, based on the specified assumptions regarding the bosutinib effect. The calculations were made using the software package PASS (2008).

Table 10-2 Detectable effect sizes for key secondary endpoint

Endpoint	Anticipated effect with bosutinib	2-sided alpha	Power	Detectable effect size [§]
MMR rate at 96 weeks	30%*	0.05	90%	≥ 23%
			80%	≥ 20%

*: [Gambacorti-Passerini et al. 2014](#), Figure 1D.

§: Absolute difference from the anticipated effect with bosutinib.

For MMR rate at 96 weeks, if the anticipated effect with bosutinib is 30%, then the given sample size with 2-sided alpha=0.05 would allow to detect an absolute difference of at least 23% (i.e. MMR rate at 96 weeks with ABL001 is at least 53%) for 90% power and of at least 20% (i.e. MMR rate at 96 weeks with ABL001 is at least 50%) for 80% power.

11 Ethical considerations and administrative procedures

11.1 Regulatory and ethical compliance

This clinical study was designed, shall be implemented and reported in accordance with the ICH Harmonized Tripartite Guidelines for Good Clinical Practice, with applicable local regulations (including European Directive 2001/20/EC and US Code of Federal Regulations Title 21), and with the ethical principles laid down in the Declaration of Helsinki.

11.2 Responsibilities of the investigator and IRB/IEC/REB

The protocol and the proposed informed consent form must be reviewed and approved by a properly constituted Institutional Review Board/Independent Ethics Committee/Research Ethics Board (IRB/IEC/REB) before study start. Prior to study start, the investigator is required to sign a protocol signature page confirming his/her agreement to conduct the study in accordance with these documents and all of the instructions and procedures found in this protocol and to give access to all relevant data and records to Novartis monitors, auditors, Novartis Clinical Quality Assurance representatives, designated agents of Novartis, IRBs/IECs/REBs and regulatory authorities as required.

11.3 Informed consent procedures

Eligible patients may only be included in the study after providing written (witnessed, where required by law or regulation), IRB/IEC/REB-approved informed consent.

Informed consent must be obtained before conducting any study-specific procedures (i.e. all of the procedures described in the protocol). The process of obtaining informed consent should be documented in the patient source documents. The date when a subject's Informed Consent was actually obtained will be captured in their eCRFs.

Novartis will provide to investigators, in a separate document, a proposed informed consent form (ICF) that is considered appropriate for this study and complies with the ICH GCP guideline and regulatory requirements. Any changes to this ICF suggested by the investigator must be agreed to by Novartis before submission to the IRB/IEC/REB, and a copy of the approved version must be provided to the Novartis monitor after IRB/IEC/REB approval.

Women of child bearing potential should be informed that taking the study medication may involve unknown risks to the fetus if pregnancy were to occur during the study and agree that in order to participate in the study they must adhere to the contraception requirement for the duration of the study. If there is any question that the patient will not reliably comply, they should not be entered in the study.

Additional consent form

Not applicable.

11.4 Discontinuation of the study

[figure not shown]
Novartis reserves the right to discontinue this study under the conditions specified in the clinical study agreement. Specific conditions for terminating the study are outlined in [Section 4.4](#).

11.5 Publication of study protocol and results

Novartis is committed to following high ethical standards for reporting study results for its innovative medicine, including the timely communication and publication of clinical trial results, whatever their outcome. Novartis assures that the key design elements of this protocol will be posted on the publicly accessible database, e.g. www.clinicaltrials.gov before study start. In addition, results of interventional clinical trials in adult patients are posted on www.novartisclinicaltrials.com, a publicly accessible database of clinical study results within 1 year of study completion (i.e., LPLV), those for interventional clinical trials involving pediatric patients within 6 months of study completion.

Novartis follows the ICMJE authorship guidelines (www.icmje.org) and other specific guidelines of the journal or congress to which the publication will be submitted

Authors will not receive remuneration for their writing of a publication, either directly from Novartis or through the professional medical writing agency. Author(s) may be requested to present poster or oral presentation at scientific congress; however, there will be no honorarium provided for such presentations.

As part of its commitment to full transparency in publications, Novartis supports the full disclosure of all funding sources for the study and publications, as well as any actual and potential conflicts of interest of financial and non-financial nature by all authors, including medical writing/editorial support, if applicable.

For the Novartis Guidelines for the Publication of Results from Novartis-sponsored Research, please refer to www.novartis.com.

11.6 Study documentation, record keeping and retention of documents

[figure not shown]
Each participating site will maintain appropriate medical and research records for this trial, in compliance with Section 4.9 of the ICH E6 GCP, and regulatory and institutional requirements for the protection of confidentiality of subjects. As part of participating in a Novartis-sponsored study, each site will permit authorized representatives of the sponsor(s) and regulatory agencies to examine (and when required by applicable law, to copy) clinical records for the purposes of quality assurance reviews, audits and evaluation of the study safety and progress.

Source data are all information, original records of clinical findings, observations, or other activities in a clinical trial necessary for the reconstruction and evaluation of the trial. Examples of these original documents and data records include, but are not limited to, hospital records, clinical and office charts, laboratory notes, memoranda, subjects' diaries or evaluation checklists, pharmacy dispensing records, recorded data from automated instruments, copies or transcriptions certified after verification as being accurate and complete, microfiches, photographic negatives, microfilm or magnetic media, x-rays, and subject files and records kept at the pharmacy, at the laboratories, and medico-technical departments involved in the clinical trial.

Data collection is the responsibility of the clinical trial staff at the site under the supervision of the site Principal Investigator. The study electronic case report form (eCRF) is the primary data collection instrument for the study. The investigator should ensure the accuracy, completeness, legibility, and timeliness of the data reported in the eCRFs and all other required reports. Data reported on the eCRF, that are derived from source documents, should be consistent with the source documents or the discrepancies should be explained. All data requested on the eCRF must be recorded. Any missing data must be explained. For electronic CRFs an audit trail will be maintained by the system.

The investigator/institution should maintain the trial documents as specified in Essential Documents for the Conduct of a Clinical Trial (ICH E6 Section 8) and as required by applicable regulations and/or guidelines. The investigator/institution should take measures to prevent accidental or premature destruction of these documents.

Essential documents (written and electronic) should be retained for a period of not less than fifteen (15) years from the completion of the Clinical Trial unless Sponsor provides written permission to dispose of them or, requires their retention for an additional period of time because of applicable laws, regulations and/or guidelines.

